### **Aims and hypotheses**

**Primary Aim 1:** To examine whether measuring unattended clinic BP with an automated device will provide a more accurate estimate of awake BP on ABPM than measuring attended clinic BP with an automated device.

**Hypothesis 1a:** The absolute difference with awake BP will be smaller for unattended vs. attended clinic BP.

**Hypothesis 1b:** The agreement between hypertension status using BP measured in the clinic and on ABPM while awake will be higher when clinic BP is measured unattended vs. attended. Also, the prevalence of both white coat and masked hypertension will be lower when measuring unattended clinic BP.

**Primary Aim 2:** To examine whether a new HBPM device provides an accurate approach for measuring sleep BP.

**Hypothesis 2a:** Sleep BP on HBPM will provide an accurate estimate of sleep BP on ABPM.

**Hypothesis 2b:** HBPM will be better tolerated (e.g., less awakening during sleep, pain, bruising) than ABPM.

**Primary Aim 3:** To compare the associations of unattended versus attending clinic BP, unattended clinic BP versus awake BP on ABPM, and sleep BP on HBPM versus ABPM with two markers of end-organ damage, left ventricular mass index (LVMI) and urinary albumin-to-creatinine ratio (ACR).

**Hypothesis 3a:** The association with end-organ damage will be stronger for unattended vs. attended clinic BP.

**Hypothesis 3b:** The association with end-organ damage will be similar for unattended clinic BP and awake BP.

**Hypothesis 3c:** The association with end-organ damage will be similar for sleep BP by HBPM and ABPM.

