  - a. **Table 4**, use a 2 x 2 table to determine the agreement hypertension on ABPM and clinic BP (i.e., HYP\_AB\_ATTEND versus HYP\_AB\_UNATTEND); provide the p-value from kappa statistics.
  - b. **Table 5**, use a 2 x 2 table to determine the agreement white coat hypertension on ABPM and clinic BP (i.e., WHIT\_AB\_ATTEND versus WHIT\_AB\_UNATTEND); provide the p-value from kappa statistics.
  - c. **Table 6**, use a 2 x 2 table to determine the agreement masked hypertension on ABPM and clinic BP (i.e., WHIT\_AB\_ATTEND versus WHIT\_AB\_UNATTEND); provide the p-value from kappa statistics.
5. Do the following analysis for **Table 7** for those with complete sleep BP data on ABPM and HBPM:
  - a. For sleep systolic BP, calculate the mean BP (with standard deviation) on ABPM and HBPM.
  - b. Calculate the absolute mean difference with 95% confidence intervals for ABPM vs. HBPM, using a paired T-test.
  - c. Repeat items 5a and 5b for sleep diastolic BP on ABPM and HBPM.
6. **Table 8**. Calculate the number and percentage of side effects and tolerability (**listed in Table 8**) that occurred in ABPM only, HBPM only, both ABPM and HBPM, and occurred for neither ABPM nor HBPM.
7. **Table 9**. Restrict the analysis to those with complete data on attended and unattended BP and complete data on left ventricular mass index .
  - a. Use linear regression to determine the relationship between attended SBP with left ventricular mass index.
  - b. Repeat the analysis for attended DBP, unattended SBP, unattended DBP with left ventricular mass index, separately.

8. **Table 10.** Restrict the analysis to those with complete BP data on unattended and awake ABPM and complete data on left ventricular mass index.
  - a. Use linear regression to determine the relationship between unattended SBP with left ventricular mass index.
  - b. Repeat the analysis for unattended DBP, awake SBP on ABPM, awake DBP on ABPM with left ventricular mass index, separately.
9. **Table 11.** Restrict the analysis to those with complete sleep BP data on ABPM and HBPM and complete data on left ventricular mass index.
  - c. Use linear regression to determine the relationship between sleep SBP on ABPM with left ventricular mass index.
  - d. Repeat the analysis for sleep DBP on ABPM, sleep SBP on HBPM, and sleep DBP on HBPM with left ventricular mass index, separately.

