10. **Table 12.** Restrict the analysis to those with complete data on attended and unattended BP and complete data on urinary albumin-to-creatinine ratio.
  - c. Use linear regression to determine the relationship between attended SBP with urinary albumin-to-creatinine ratio.
  - d. Repeat the analysis for attended DBP, unattended SBP, unattended DBP with urinary albumin-to-creatinine ratio, separately.
11. **Table 13.** Restrict the analysis to those with complete BP data on unattended and awake ABPM and complete data on urinary albumin-to-creatinine ratio.
  - e. Use linear regression to determine the relationship between unattended SBP with urinary albumin-to-creatinine ratio.
  - f. Repeat the analysis for unattended DBP, awake SBP on ABPM, awake DBP on ABPM with urinary albumin-to-creatinine ratio, separately.
12. **Table 14.** Restrict the analysis to those with complete sleep BP data on ABPM and HBPM and complete data on urinary albumin-to-creatinine ratio.
  - g. Use linear regression to determine the relationship between sleep SBP on ABPM with urinary albumin-to-creatinine ratio.
  - h. Repeat the analysis for sleep DBP on ABPM, sleep SBP on HBPM, and sleep DBP on HBPM with urinary albumin-to-creatinine ratio, separately.

Table 1. Characteristics of Better BP participants by randomization.

	Overall N = 603	Attended then unattended, N = 301	Unattended then attended, N = 302	ABPM then HBPM, N = 302	HBPM then ABPM, N = 301
Age, yrs,					
Mean (SD)	38.6 (15.1)	39.4 (16.0)	37.9 (14.1)	39.2 (15.7)	38.1 (14.5)
Median (min – max)	34.0 (18.0 - 83.0)	35.0 (19.0 - 83.0)	34.0 (18.0 - 83.0)	35.5 (18.0 - 79.0)	33.0 (19.0 - 83.0)
Women, %	382 (63.3)	190 (63.1)	192 (63.6)	191 (63.2)	191 (63.5)
Race, %					
Hispanic	39 (6.5)	24 (8.0)	15 (5.0)	22 (7.3)	17 (5.6)
Non-Hispanic, Asian	90 (14.9)	39 (13.0)	51 (16.9)	47 (15.6)	43 (14.3)
Non-Hispanic, Black	132 (21.9)	64 (21.3)	68 (22.5)	61 (20.2)	71 (23.6)
Non-Hispanic, White	291 (48.3)	150 (49.8)	141 (46.7)	148 (49.0)	143 (47.5)
Other non-Hispanic race/ethnicity	51 (8.5)	24 (8.0)	27 (8.9)	24 (7.9)	27 (9.0)
Body Mass Index					
Mean (SD)	27.2 (5.9)	26.8 (5.9)	27.5 (5.8)	27.2 (5.6)	27.2 (6.1)
Median (min – max)	25.9 (13.0 - 55.5)	25.6 (13.0 - 55.5)	26.5 (17.2 - 53.0)	26.0 (13.0 - 53.0)	25.9 (17.3 - 55.5)
Attended office blood pressure					
Systolic BP					
Mean (SD)	119.4 (12.0)	118.9 (12.1)	120.0 (12.0)	119.7 (11.9)	119.2 (12.2)

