Attended clinic systolic BP	-0.2	-0.47	0.08	0.14	-1.39	0.17	-0.06
Attended clinic diastolic BP	-0.28	-0.7	0.15	0.22	-1.27	0.20	-0.05
Unattended clinic systolic BP	-0.26	-0.55	0.02	0.14	-1.84	0.07	-0.08
Unattended clinic diastolic BP	-0.37	-0.8	0.06	0.22	-1.68	0.09	-0.07

Dependent variable: urinary albumin-to-creatinine ratio (mg/g) as continuous variable

**Table 13.** The relationship between unattended clinic BP versus awake BP on ABPM with urinary albumin-to-creatinine ratio (mg/g), N=523.

Model	Unstandardized beta	Lower limit of 95% confidence intervals for beta	Upper limit of 95% confidence intervals for beta	Standard Error	t-statistic	P-value	Standardized beta
Unattended systolic BP	-0.18	-0.44	0.07	0.13	-1.39	0.16	-0.06
Unattended diastolic BP	-0.09	-0.49	0.31	0.20	-0.45	0.65	-0.02
Awake systolic BP on ABPM	0.01	-0.29	0.31	0.15	0.07	0.94	0.00
Awake diastolic BP on ABPM	0.22	-0.21	0.66	0.22	1.01	0.31	0.04

**Table 14.** The relationship between sleep BP on H BPM versus ABPM with urinary albumin-to-creatinine ratio (mg/g), N=505.

Model	Unstandardized beta	Lower limit of 95% confidence intervals for beta	Upper limit of 95% confidence intervals for beta	Standard Error	t-statistic	P-value	Standardized beta
Sleep systolic BP on H BPM	-0.01	-0.28	0.26	0.14	-0.08	0.94	-0.00
Sleep diastolic BP on H BPM	-0.02	-0.40	0.36	0.20	-0.09	0.93	-0.00
Sleep systolic BP on ABPM	0.09	-0.21	0.40	0.15	0.61	0.54	0.03
Sleep diastolic BP on ABPM	0.26	-0.16	0.68	0.21	1.20	0.23	0.05

Dependent variable: urinary albumin-to-creatinine ratio (mg/g) as continuous variable

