**Hypothesis 3a:** The association with end-organ damage will be stronger for unattended vs. attended clinic BP.

**Hypothesis 3b:** The association with end-organ damage will be similar for unattended clinic and awake BP.

**Hypothesis 3c:** The association with end-organ damage will be similar for sleep BP by HBPM and ABPM.

Below we describe the analysis plan for testing Hypothesis 3a. The analysis plan will be identical for Hypotheses 3b and 3c. We will calculate the intraclass correlation coefficients between (1) attended clinic BP and (2) unattended clinic BP with LVMI. The statistical significance of the difference in the correlation coefficients will be calculated using the Fisher r-to-z transformation accounting for the within-person correlation between unattended and attended BP measurements. Also, the association between clinic BP, measured unattended and attended, separately, and LVMI will be calculated using linear regression. For these models, clinic BP will be modeled in categories, using restricted quadratic splines, and, if appropriate, as a continuous variable (e.g., per 10 mm Hg higher SBP). Two levels of adjustment will be performed as described in **Section D.11.2.**

For secondary testing of Hypothesis 3, we will model the outcome of LVH defined as an  $\text{LVMI} \geq 96 \text{ g/m}^2$  in women and  $\text{LVMI} \geq 116 \text{ g/m}^2$  in men using Poisson regression with robust standard errors and two levels of adjustment (**Section D.11.2**). The analyses will be repeated for the outcome of the ACR. When modeled as a continuous variable, ACR will be log-transformed due to its skewed distribution. As a dichotomous variable, albuminuria will be defined as an sex/race-adjusted  $\text{ACR} > 25 \text{ mg/g}$ .

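### Aim 3 asserts that BP associations are stronger or similar, but Analysis Plan items 7–12 give no interval or test for any difference between BP measures

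*Combined protocol and SAP*

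**What the plan says.** **Analysis Plan.** Hypothesis 3a is that "The association with end-organ damage will be stronger for unattended vs. attended clinic BP". Hypotheses 3b and 3c state that the associations are similar for unattended clinic and awake BP, and for sleep BP by HBPM and by ABPM. For LVMI, item 7 says "Use linear regression to determine the relationship between attended SBP with left ventricular mass index" and repeats this for each other BP measure separately; items 8 and 9 follow the same pattern. For ACR, item 10 says "Use linear regression to determine the relationship between attended SBP with urinary albumin-to-creatinine ratio", and items 11 and 12 follow. The footnotes to Tables 12 and 14 give the outcome as "urinary albumin-to-creatinine ratio (mg/g) as continuous variable". No item names a covariate, and Tables 9–14 have no column comparing two measures.

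**Section D.11.6 (research plan).** Written for 3a, this section starts from correlations with the outcome: "We will calculate the intraclass correlation coefficients between (1) attended clinic BP and (2) unattended clinic BP with LVMI". It then plans the comparison that the Analysis Plan lacks: "The statistical significance of the difference in the correlation coefficients will be calculated using the Fisher r-to-z transformation accounting for the within-person correlation", so that the test allows for both BP measures coming from the same person. The other two hypotheses are covered by a single line: "The analysis plan will be identical for Hypotheses 3b and 3c". Regressions were to carry the two adjustment levels of D.11.2, the first being age, race/ethnicity, sex and site. The analyses were to be repeated for ACR, on a different scale from the one now used: "When modeled as a continuous variable, ACR will be log-transformed due to its skewed distribution". Table 7 in D.12.3 states Aim 3 power as detectable differences between correlations.

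**The concern.** Two slopes estimated separately do not show that one association is stronger than, or similar to, the other. That needs an estimate of the difference with its uncertainty. Both measures come from the same people, so the uncertainty of the difference depends on how closely they correlate. Two CIs read side by side ignore this and hide most of the available precision. In Tables 9–11 every LVMI coefficient has a p-value of 0.01 or less. A reader could take that list as support for 3a, 3b or 3c, although none of those p-values addresses a difference between measures.

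Two secondary matters are separate from this. D.11.6 gave skewness as its reason for logging ACR; on the mg/g scale a few high values can dominate a least-squares slope. Unadjusted slopes also carry whatever age, sex, race/ethnicity and site contribute.

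**Working it through.** **1. The planned power figure is for the omitted test.** Inputs from D.12.3: n = 600, correlation between BP measures ρ = 0.5, correlation with LVMI 0.30, 80% power, two-sided 5%. Steiger's test for dependent correlations is

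z = (atanh r₁ − atanh r₂)·√(n−3) / √(2−2c), with c = [ρ(1−2m²) − ½m²(1−2m²−ρ²)] / (1−m²)² and m the mean of r₁ and r₂.

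Solving for 80% power gives a detectable difference of 0.105, against the stated 0.11. The other five n = 600 cells also reproduce: 0.091, 0.080, 0.083, 0.073 and 0.065, against 0.09, 0.08, 0.08, 0.07 and 0.07.

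**2. What was fitted.** With one predictor, the standardized beta equals r = t/√(t²+n−2). Attended SBP in Table 9: 7.55/√(7.55²+585) = 0.298, printed 0.30. All 24 rows of Tables 9–14 agree to rounding, as unadjusted models would. For ACR, outcome SD ≈ SE × SD(BP) × √N, with SE = CI width/(2 × 1.964). Unattended SBP in Table 12: SE = 0.57/3.928 = 0.145; 0.145 × 11.8 × √555 ≈ 40. This is plausible in mg/g but not on a log scale.

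**3. Correlation between BP measures.** From Analysis Plan Tables 2 (N = 569) and 7 (N = 547): SD of the difference = CI width × √N/(2 × 1.964), and ρ = (s₁²+s₂²−SD²)/(2s₁s₂). Attended versus unattended SBP: 0.60 × √569/3.928 = 3.64; ρ = (12.1² + 11.9² − 3.64²)/(2 × 12.1 × 11.9) = 0.954. The other values of ρ, obtained the same way, are in the table below.

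**4. The missing LVMI contrasts.** Correlations come from the printed t-statistics, p from Steiger's z, and CIs from Zou's method. Values are approximate and unadjusted.

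| Contrast | n | ρ | r₁ vs r₂ | Difference (95% CI) | p |
|---|---|---|---|---|---|
| 3a SBP, unattended − attended | 587 | 0.954 | 0.296 vs 0.298 | -0.002 (-0.025, 0.022) | 0.88 |
| 3a DBP | 587 | 0.941 | 0.165 vs 0.189 | -0.024 (-0.052, 0.003) | 0.08 |
| 3b SBP, unattended − awake | 554 | 0.763 | 0.300 vs 0.347 | -0.047 (-0.101, 0.007) | 0.09 |
| 3b DBP | 554 | 0.689 | 0.167 vs 0.182 | -0.015 (-0.080, 0.050) | 0.65 |
| 3c SBP, HBPM − ABPM | 533 | 0.63–0.72 | 0.211 vs 0.277 | -0.065; CI from (-0.136, 0.005) to (-0.127, -0.004) | 0.07 to 0.04 |
| 3c DBP | 533 | 0.661 | 0.110 vs 0.156 | -0.046 (-0.116, 0.023) | 0.19 |

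For 3c SBP, rounding in Table 7 leaves ρ anywhere from 0.63 to 0.72, so whether the interval excludes zero is undetermined.

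**5. What pairing is worth.** For 3a SBP the paired half-width is about 0.024. Treating the correlations as independent gives √2 × 1.96 × (1−0.297²)/√584 = 0.105.

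**6. Raw ACR.** From Table 12 (N = 555) to Table 13 (N = 523) the unattended DBP slope moves from -0.37 to -0.09 and the SBP slope from -0.26 to -0.18. If the 523 are nested in the 555, BP variance is equal and loss is random, the expected SD of the shift is SE × √(N₁/N₂ − 1).
- DBP: 0.219 × √(555/523 − 1) = 0.054, so the shift of 0.28 is 5.2 SDs (4.9–5.4 with rounding).
- SBP: 0.145 × 0.247 = 0.036, so the shift of 0.08 is 2.2 SDs (1.9–2.6).
- The matching LVMI slopes (Tables 9 and 10) move by 0.4 and 0.0 SDs.

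**The case against.** **A like-for-like comparison is already printed.** Items 7–12 restrict each pair to people with both measures, and in one-predictor models the standardized betas are the correlations. Objective 6 asks only that the associations be determined. This stands as mitigation: the descriptive comparison exists. It does not supply inference on the difference, which the hypotheses need.

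**Section D is a funding proposal, partly superseded.** The clinic device and the fasting blood draw changed. For ACR itself, D.8.7 plans a sex- and race-adjusted ratio with a 25 mg/g cut-point, while the manual lists a plain ratio and the results packet uses 30 mg/g. D.11.2 is also worded as a general intention. A reader might infer a breach of a binding protocol. The documents do not support that, because they never settle the standing of D.11.6. They also never say that it was replaced, or why. The main point does not depend on it, since the Analysis Plan restates 3a–3c as its own hypotheses.

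**Raw ACR and absent covariates do not leave the hypotheses untested.** Correct; only the missing comparison does that. With ρ near 0.95 for 3a, shared covariates should act almost equally on both slopes, and nothing in the documents shows that adjustment would change that contrast.

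**The ACR shift has other explanations.** Non-random loss of people without complete ABPM could produce it, and logging would not repair that. A reader might infer that outliers demonstrably drove the ACR results; the tables are only consistent with that.

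**Conclusion.** The concern holds for the missing comparison. On the Analysis Plan's own terms, 3a–3c are stated but not tested, and the Aim 3 power statement refers to a test that items 7–12 do not include. The unlogged ACR and the absent covariates are secondary, unexplained departures from D.11.6 and D.11.2, and their effect on the results is not quantified.

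The recovered contrasts show what is unreported and are not conclusions. They rest on rounded table values and on BP correlations from samples of 569 and 547 being carried over to the LVMI samples. A reader might infer that the data contradict 3a, or that HBPM is shown to be inferior under 3c. Neither follows: the 3a DBP interval includes zero, and for 3c SBP the exclusion of zero is undetermined. Nor would a non-significant difference establish 3b or 3c, because neither part of the document states a margin for similarity. This should be fixed; it does not invalidate the fits already tabulated.

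**What to change.** 1. Add to items 7–12 the difference between dependent Pearson correlations, or a bootstrapped difference in standardized slopes, with 95% CI. Do this for SBP and DBP, for LVMI and ln(ACR), and for each of 3a–3c. Pearson should replace the intraclass correlation named in D.11.6, because BP and LVMI have different units. This makes 3 × 2 × 2 = 12 comparisons, so state that they are multiple.
2. Use ln(ACR) in items 10–12, with a rule for zero or below-limit values, and say whether the D.8.7 sex/race factor applies. Keep the mg/g fits as descriptive.
3. Report D.11.2's first model beside the unadjusted fits, including site only if it varies in the data (Table 1 has no site row). Fit the second model only with covariates actually collected, and name those dropped. Check stress (on the Visit 1 form but not in the REDCap instrument list), anxiety (added in the supplement) and outdoor temperature (only in D.8.3.4 and D.11.2).
4. For 3b and 3c, report the CI. Do not claim similarity from a non-significant difference or from a margin chosen after the results.
5. Document the change from D.11.6, and that it was made after results were tabulated.

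The cost is wording and a re-run. The plan provides for collecting BP, LVMI, ACR, age, sex and race/ethnicity. The price is ratio-scale ACR coefficients, a low-value rule and analyses that must be labelled post hoc.

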#### **Statistical analysis:**

1. Calculate the distribution of the variables in **Table 1**, overall, and separately for participants who were attended then unattended, unattended then attended, as well as participants who underwent ABPM before HBPM, and HBPM before ABPM.
2. Do the following analysis for **Table 2** for those with complete BP data on ABPM, attended, and unattended:
  - a. For awake systolic BP, calculate the mean (with standard deviation) BP on ABPM, attended, and unattended
  - b. Calculate the absolute mean difference with 95% confidence intervals for ABPM vs. attended, ABPM vs. unattended, and attended vs. unattended, using mixed model to determine the difference between the differences.
  - c. Repeat items **2a** and **2b** for awake diastolic BP on ABPM, attended and unattended.

3. Do the following analysis for **Table 3** for those with complete BP data on ABPM, attended, and unattended:
  - a. Calculate the percentage (with 95% confidence interval) of participants with hypertension on awake ABPM (i.e., ABPM\_HYPER = 1)
  - b. Calculate the percentage (with 95% confidence interval) of participants with hypertension on attended BP measurements (i.e., ATTENDED\_HYPER = 1).
  - c. Calculate the percentage (with 95% confidence interval) of participants with hypertension on unattended BP measurements (i.e., UNATTENDED\_HYPER = 1).
  - d. Calculate the percentage (with 95% confidence intervals) of participants with hypertension on attended and awake ABPM (i.e., HYP\_AB\_ATTEND = 1).
  - e. Calculate the percentage (with 95% confidence intervals) of participants with hypertension on unattended and awake ABPM (i.e., HYP\_AB\_UNATTEND = 1).
  - f. Calculate the percentage (with 95% confidence intervals) of participants with white coat hypertension on ABPM and attended BP (i.e., WHIT\_AB\_ATTEND = 1).
  - g. Calculate the percentage (with 95% confidence intervals) of participants with white coat hypertension on ABPM and unattended BP (i.e., WHIT\_AB\_UNATTEND = 1)
  - h. Calculate the percentage (with 95% confidence intervals) of participants with masked hypertension on ABPM and attended BP (i.e., MASK\_AB\_ATTEND = 1).
  - i. Calculate the percentage (with 95% confidence intervals) of participants with masked hypertension on ABPM and unattended BP (i.e., MASK\_AB\_UNATTEND = 1)
4. Do the following analysis for those with complete BP data on ABPM, attended, and unattended:

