Monitor interfered with normal sleeping pattern	124 (20.6)	56 (9.3)	219 (36.3)	204 (33.8)
Removed monitor due to disturbance while sleeping	23 (3.8)	23 (3.8)	16 (2.7)	541 (89.7)

**Table 9.** The relationship between attended and unattended clinic BP with left ventricular mass index (g/m^2), N=587.

Model	Unstandardized beta	Lower limit of 95% confidence intervals for beta	Upper limit of 95% confidence intervals for beta	Standard Error	t-statistic	P-value	Standardized beta
Attended clinic systolic BP	0.43	0.32	0.55	0.06	7.55	<.001	0.30
Attended clinic diastolic BP	0.42	0.24	0.60	0.09	4.66	<.001	0.19
Unattended clinic systolic BP	0.44	0.33	0.56	0.06	7.50	<.001	0.30
Unattended clinic diastolic BP	0.37	0.19	0.55	0.09	4.04	<.001	0.16

Dependent variable: left ventricular mass index (g/m^2) as continuous variable

**Table 10.** The relationship between unattended clinic BP versus awake BP on ABPM with left ventricular mass index (g/m^2), N=554

Model	Unstandardized beta	Lower limit of 95% confidence intervals for beta	Upper limit of 95% confidence intervals for beta	Standard Error	t-statistic	P-value	Standardized beta
Unattended systolic BP	0.44	0.32	0.56	0.06	7.38	<0.001	0.30
Unattended diastolic BP	0.38	0.19	0.56	0.09	3.99	<0.001	0.17
Awake systolic BP on ABPM	0.61	0.47	0.74	0.07	8.69	<0.001	0.35
Awake diastolic BP on ABPM	0.45	0.25	0.66	0.10	4.36	<0.001	0.18

Dependent variable: left ventricular mass index (g/m^2) as continuous variable

**Table 11.** The relationship between sleep BP on H BPM versus ABPM with left ventricular mass index (g/m^2), N=533

Model	Unstandardized beta	Lower limit of 95% confidence intervals for beta	Upper limit of 95% confidence intervals for beta	Standard Error	t-statistic	P-value	Standardized beta
Sleep systolic BP on H BPM	0.31	0.19	0.44	0.06	4.98	<0.001	0.21
Sleep diastolic BP on H BPM	0.23	0.05	0.40	0.09	2.54	0.01	0.11
Sleep systolic BP on ABPM	0.45	0.32	0.59	0.07	6.63	<0.001	0.28
Sleep diastolic BP on ABPM	0.36	0.16	0.55	0.10	3.64	<0.001	0.16

Dependent variable: left ventricular mass index (g/m^2) as continuous variable

**Table 12.** The relationship between attended and unattended clinic BP with urinary albumin-to-creatinine ratio (mg/g), N=555.

Model	Unstandardized beta	Lower limit of 95% confidence intervals for beta	Upper limit of 95% confidence intervals for beta	Standard Error	t-statistic	P-value	Standardized beta

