**Table 6. Phenotypes to be evaluated in the proposed study.**

Phenotype	Attended clinic SBP/DBP	Unattended clinic SBP/DBP	Out-of-clinic SBP/DBP
White coat Hypertension	$\geq 140/90$ mm Hg	$\geq 135/85$ mm Hg	Awake $< 135/85$ mm Hg
Masked Hypertension	$< 140/90$ mm Hg	$< 135/85$ mm Hg	Awake $\geq 135/85$ mm Hg
Nocturnal Hypertension	Not applicable	Not applicable	Sleep $\geq 120/70$ mm Hg

**D.11. Statistical analysis.** All data will be analyzed by a statistician blinded to participants' randomization assignments and a code (e.g., 0 or 1) will be used to represent different randomization assignments.

Assignments will be unmasked after completion of the statistical analyses. The distribution of each BP measure, covariate, and echocardiographic measure will be calculated. Variables will be explored for outliers and when identified the staff in the field sites will be asked to investigate them further.

**D.11.1 Missing data.** Missingness in our prior studies has been uncommon. Our primary approach to missing data is to collect complete data. We will examine missing data and use multiple imputation, as appropriate.

**D.11.2 Multivariable adjustment.** Several analyses will include multivariable adjustment. Multivariable adjustment will be guided by biologic plausibility and will be contingent on the specific hypothesis being tested. In general, we plan two levels of adjustment. An initial model will include adjustment for age, race/ethnicity, sex and clinic site (UAB or Columbia). A second model will include additional adjustment for education, body mass index, smoking, physical activity, alcohol consumption, stress, anxiety, outdoor temperature, sleep quality, diabetes, eGFR, and 10-year predicted CVD risk. Co-linearity will be assessed using variable inflation factors.

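### The Analysis Plan neither examines missing data nor imputes, as protocol section D.11.1 foresaw, and the same ACR slope on unattended diastolic BP prints as -0.37 in Table 12 and -0.09 in Table 13

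*Combined protocol and SAP*

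**What the plan says.** Section D.11.1 of the protocol opens with prevention: "Our primary approach to missing data is to collect complete data". It continues: "We will examine missing data and use multiple imputation, as appropriate". The condition attaches to the imputation; the examination of missing data is stated without one.

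The Analysis Plan mentions neither step. Its items 2 to 5 and 7 to 12 restrict to complete cases:

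- Tables 2 to 6 share one set of 569, defined as "for those with complete BP data on ABPM, attended, and unattended".
- Table 7 uses 547.
- Tables 9 to 14 use 587, 554, 533, 555, 523 and 505, one set per table.
- Tables 1 and 8 use all 603.

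For Table 12 the rule is "Restrict the analysis to those with complete data on attended and unattended BP and complete data on urinary albumin-to-creatinine ratio". For Table 13 it is "Restrict the analysis to those with complete BP data on unattended and awake ABPM and complete data on urinary albumin-to-creatinine ratio". The titles give the sizes: "The relationship between attended and unattended clinic BP with urinary albumin-to-creatinine ratio (mg/g), N=555" and "The relationship between unattended clinic BP versus awake BP on ABPM with urinary albumin-to-creatinine ratio (mg/g), N=523".

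The two tables have one pair of models in common, ACR on unattended clinic systolic and diastolic BP. The diastolic row of Table 12 reads "Unattended clinic diastolic BP -0.37 -0.8 0.06 0.22 -1.68 0.09 -0.07" (slope, confidence limits, SE, t, P, standardised slope). The matching row of Table 13 gives -0.09, limits -0.49 and 0.31, SE 0.20, t -0.45 and P 0.65.

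Section D.11.6 says that ACR as a continuous outcome is to be log-transformed because it is skewed. Analysis Plan items 10 to 12 name no transformation, and the tables report mg/g.

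**The concern.** A step that the protocol foresaw has gone without a stated reason, and the circumstances that would call for it are present. Section D.11.1 rests on missingness having been uncommon in prior studies, and section D.12.1 allows for 30 of 630 not completing. The loss in Tables 9 to 14 reaches 98 of 603. Nothing in the Analysis Plan describes who is missing.

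The Aim 3 hypotheses are then read from different sets of people. Hypothesis 3a takes its unattended ACR slope from Table 12 and hypothesis 3b from Table 13. For diastolic BP these two estimates of one quantity are far apart, and the reader is given nothing with which to explain the gap.

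**Working it through.** **Inputs.** Slopes, limits, SEs and Ns come from Tables 9, 10, 12 and 13. The SDs of unattended BP are 7.7 (diastolic) and 11.8 (systolic) mm Hg, from Table 1 (N=603), and are assumed to hold in the subsets.

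**1. Reproduce the printed rows.** t = slope/SE; limits = slope ± t(0.975, N-2) × SE.
- Table 12: -0.37/0.22 = -1.68; limits -0.80 to 0.06; P = 0.094.
- Table 13: -0.09/0.20 = -0.45; limits -0.48 to 0.30; P = 0.653.

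Both agree with the printed rows within rounding.

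**2. Loss from 603.** Table 7: 56 (9.3%). Tables 9 to 14: 16 (2.7%), 49 (8.1%), 70 (11.6%), 48 (8.0%), 80 (13.3%) and 98 (16.3%).

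**3. Size of the shift.** 555 - 523 = 32 (5.8% of 555). The diastolic slope moves by 0.28, which is 0.28/0.22 = 1.27 of the Table 12 SE. The systolic slope moves by 0.08, from -0.26 to -0.18.

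**4. Random-loss yardstick.** If the smaller set is nested in the larger, the loss is random and the residual variance is constant, the SD of the change is SE × sqrt(555/523 - 1).
- Diastolic: 0.22 × 0.247 = 0.054, and 0.28/0.054 is about 5.
- Systolic: 0.14 × 0.247 = 0.035, and 0.08/0.035 is about 2.3.

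**5. Does the constant-variance assumption hold?** Under it, the diastolic SE should rise to 0.22 × sqrt(555/523) = 0.227. It falls to 0.20. Taking the SE from the width of the interval, residual SD = SE × 7.7 × sqrt(N-1):
- Table 12: 0.2189 × 7.7 × sqrt(554) = 39.7 mg/g.
- Table 13: 0.2036 × 7.7 × sqrt(522) = 35.8 mg/g.

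The residual sums of squares are about 39.67² × 553 = 870,000 and 35.82² × 521 = 668,000. The 32 people thus carry about 202,000, or 23%. Rounding of the printed limits makes this roughly 19% to 27%.

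**6. Could one person do it?** Give 31 of the 32 the typical squared residual: 31 × 1,283 = 39,800. That leaves about 162,000, a single residual of about 400 mg/g. Put that person 23 mm Hg below the mean diastolic and 15 below the mean systolic BP:
- Diastolic shift: 400 × 23/(554 × 7.7²) = 9,200/32,847 = 0.28.
- Systolic shift: 400 × 15/(554 × 11.8²) = 6,000/77,139 = 0.08.

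Both shifts are reproduced. The values lie inside Table 1's ranges: 72.2 - 23 = 49.2 against a minimum of 47.2, and 118.7 - 15 = 103.7 against 90.5. Any given person falls in a random 32 of 555 with probability 5.8%.

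**7. Comparator.** For LVMI, N falls from 587 (Table 9) to 554 (Table 10), a net loss of 33. The unattended slopes go from 0.37 to 0.38 (diastolic) and from 0.44 to 0.44 (systolic). The same yardstick for diastolic is 0.09 × sqrt(587/554 - 1) = 0.022, so a change of 0.01 is unremarkable.

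**The case against.** Imputation was conditional, and the protocol builds in completeness by other means: thresholds for an adequate recording (D.10.4), repeat monitoring, and a sample sized on complete data. Each Aim 3 comparison is made within one table, on the same people, which is a normal paired choice. This stands. A reader might infer that a firm commitment to impute was broken; the wording of D.11.1 does not support that. What remains is that the examination of missing data was not conditional and that no reason is given for leaving out either step.

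A reader might also infer, from a shift of about five random-loss SDs, that the people dropped differ as a group, or that those who tolerated monitoring were selected. The documents do not support this. The yardstick fails for a skewed outcome, one extreme value suffices (step 6), and no reasons for missing ABPM data are given. Nesting is likely but unproven, because Table 13 does not require attended BP; 32 is a net difference.

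Finally, imputation alone would not cure the instability. The people without complete ABPM in Table 12 already have observed clinic BP and ACR, so imputing awake BP would return the unattended slope to about its Table 12 value, with any outlier back in. That also stands, and it is why the log scale belongs in the remedy.

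**Conclusion.** The point holds as an omission with a visible symptom. The Analysis Plan leaves out the examination of missing data and the imputation foreseen in D.11.1, without explanation, while its Aim 3 tables lose 2.7% to 16.3% of 603. A net loss of 32 people shrinks one slope by about 76% (0.28/0.37), most plausibly because one or a few very high ACR values leave the set.

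The limits are equally plain. Neither slope is significant, the intervals overlap and no test result changes. This is the most extreme pair, and the LVMI slopes are stable. Untransformed ACR probably contributes, and log-ACR might remove much of the shift. A reader might infer that the conclusion on hypothesis 3b is altered, but the documents do not show where the awake slope would fall in the larger set. The influence figures assume nesting and a BP spread equal to Table 1's. No post-imputation slope can be calculated without participant data.

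**What to change.** - **Describe the missing.** Compare included with excluded participants on baseline characteristics, clinic BP, LVMI and ACR, for each analysis set.
- **Aim 3 (Tables 9 to 14).** Use log-ACR as D.11.6 states. Add a multiple-imputation analysis on one common set of 603. The imputation model should use both visits' clinic BP, any partial ABPM or HBPM readings, baseline covariates, site and both randomised orders. Print it beside the complete-case results.
- **Tables 2 to 7.** Keep complete cases as primary, since the missing value is often the reference measurement itself. Imputation is at most a sensitivity analysis here.
- **Labelling.** State that these analyses were added after results were available.

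The cost is Analysis Plan wording and modest programming. The scientific price is reliance on data being missing at random, which the side-by-side complete-case results expose, and an imputation model specified after results were seen, which the label discloses.
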